Protocol H9X-IN-GBGR titled “A 24-week multicenter, open-label, single-arm study to evaluate safety in patients with type 2 diabetes mellitus in India treated with dulaglutide” has been amended. The new protocol is indicated by Amendment (b) and will be used to conduct the study in place of any preceding version of the protocol.

The overall changes and rationale for the changes made to this protocol are described in the following table:

Section Number and Name	Description of Change	Brief Rationale
Section 1.3 Schedule of Activities	Marked X for AEs in Screening column	Corrected the error.
	Added “temperature” in Vital signs	Corrected the error.
	Removed “insulin dose (if the patient is taking insulin)” in Diary compliance check	Patient Diary does not have a provision of capturing Insulin Dose. Insulin dose can be captured in source document (eCRF)
Section 2.1 Study Rationale	Deleted “combination therapy” for 0.75mg in Study Rationale.	0.75 mg is not recommended as a combination therapy in the label - it is only approved as a monotherapy- since 0.75 mg dose is approved, one can maintain the patient on this if the patient is not able to tolerate 1.5 mg for some reason or as is common practice, one can start on 0.75 mg and build up the dose to 1.5 mg.

Section Number and Name	Description of Change	Brief Rationale
Figure 6.1	For GI Side effects, - Yes, superscript “a” was added to clarify.	Corrected the error.
Section 6.5 Dose modification	Updated language by adding “permitted only once”.	There could be a titration in the initial part of the study as explained in the dispensing scenarios which usually covers the first 4-6 weeks in the study. Thereafter and once this happens, this titration is not allowed beyond that period.
Section 6.8 Concomitant therapy	Replaced the hypoglycemia word to “hyperglycemia”	The chances of developing hypoglycemia with dulaglutide per se is less. However, if there is an occasional hypoglycemia in a patient following dulaglutide start, the concomitant dose of SU and or insulin should be modified as per the PI discretion.
Section 7.1.3 Temporary Discontinuation	Updated the language to “allowed once” and added that “Study drug discontinuation decision will be taken post the titration in the initial 4-6 weeks of the study”	Corrected the error. Study drug discontinuation decision will be taken post the titration in the initial 4-6 weeks of the study.

1.1. Synopsis

Protocol Title:

A 24-week multicenter, open-label, single-arm study to evaluate safety in patients with type 2 diabetes mellitus in India treated with dulaglutide.

Brief Title:

A study to investigate adverse and serious adverse events with dulaglutide in participants with type 2 diabetes mellitus in India.

Regulatory Agency Identifier Number: Not applicable

Rationale:

Once weekly dulaglutide was approved on 23 December 2014 by CDSCO. As per the approved label in India, once-weekly 1.5 mg dulaglutide is recommended as a combination therapy in patients with T2DM in addition to the ongoing OHAs and/or insulin. In select cases, for example, in patients with metformin intolerance, 0.75 mg dulaglutide is recommended as monotherapy. The CDSCO had stipulated a Phase 4 study to document the experience of the local population with T2DM from India as a clause toward marketing authorization for dulaglutide in India. A Phase 4 observational study to assess the safety including AEs and SAEs with dulaglutide in patients with T2DM India is currently ongoing. This Phase 4 clinical study, over and above the observational study, is being proposed to fulfill this marketing authorization clause.

Objectives and Endpoints:

Objectives	Endpoints
Primary	
Assess the safety profile of 1.5 and 0.75 mg dulaglutide in patients with T2DM in India	Incidence of AEs (deaths, SAEs, TEAEs, and hypoglycemia, including severe hypoglycemia) Proportion of patients reporting AEs and SAEs between baseline and Week 24 Incidence of GI AEs
Secondary	
Change in HbA1c for pooled doses of dulaglutide	Mean change in HbA1c from baseline to Week 24
Exploratory	
Change in body weight	Mean change in body weight from baseline to Week 24
Change in FBG	Mean change in FBG from baseline to Week 24
Change in vital signs	Change in systolic blood pressure, diastolic blood pressure, and pulse rate from baseline to Week 24

Overall Design

This is a Phase 4, single-arm study to study the safety of dulaglutide in patients with T2DM in India who are on stable doses of oral antihyperglycemic medications with or without stable doses

of basal or premix insulin for the last 3 months prior to screening. The efficacy profile of dulaglutide will be measured as a secondary endpoint.

Brief Summary:

The purpose of this study is to assess the safety profile of 1.5 and 0.75 mg dulaglutide in patients with T2DM in India.

The study includes a

- Screening Visit
- 2-week lead-in period
- 24-week treatment period, and
- follow-up period 4 weeks after the last treatment.

Study Population:

In general, participants may take part in the study if they

- are 18 years of age or older, at the time of signing the informed consent
- reside in India
- have a diagnosis of T2DM of at least 1-year duration currently treated with stable doses of oral antihyperglycemic medications with or without stable doses of basal or premix insulin for the last 3 months prior to screening. Premix insulin is allowed up to twice daily in the screening period to be taken up further. Doses of other OHAs will be optimized as per investigator's discretion. Patients on thrice-daily premix insulin or full basal bolus insulin (insulin regimen 3-4 times daily) therapy are excluded from the study
- have HbA1c $\geq 7.5\%$ and $\leq 11.5\%$, both inclusive, at screening, and
- have BMI $\geq 23 \text{ kg/m}^2$.

In general, participants may not take part in the study if they have

- a diagnosis of T1DM or latent autoimmune diabetes, or specific type of diabetes other than T2DM
- been treated with antihyperglycemic medication like GLP-1 RA or have a prior history of any contraindication to GLP-1 RA therapy within 3 months prior to screening, or
- eGFR $< 15 \text{ ml/min/1.73m}^2$.

Number of Participants:

An estimated 250 participants will be screened, and assuming a 20% screen failure rate, an estimated 200 participants will be initiated on IP. Assuming a 20% dropout rate by the end of the study period, approximately 160 patients at the end of the study would allow for an adequate description of AEs and other safety outcomes. This is required to fulfill the market authorization clause.

Intervention Groups and Duration:

This table lists the intervention used in this clinical study.

Intervention Name	Dulaglutide
Dosage Levels	0.75 or 1.5 mg
Route of Administration	Subcutaneous injection
Frequency of Administration	Once weekly

The following circumstances are permitted:

[figure not shown]
1. Treatment will be started with dulaglutide 1.5 mg as combination therapy or dulaglutide 0.75 mg as combination therapy or monotherapy. For patients who report GI AEs after starting treatment with 1.5 mg dulaglutide, the investigator may reduce the dose to 0.75 mg based on symptoms reported by patients. Treatment will be continued with 0.75 mg for 2 to 3 weeks. Thereafter, the 1.5-mg dose will be reintroduced.
2. As per common practice in India, treatment may be started with 0.75 mg dulaglutide as a combination therapy in select cases (Wasir et al. 2018). The dose may be up titrated to 1.5 mg after a period of 2 to 4 weeks in consultation with the medical monitor.

Ethical Considerations of Benefit/Risk:

Considering the clinical data to date and measures taken to minimize risk for the participants in this study, the potential risks identified in association with dulaglutide are justified by the anticipated benefits that may be afforded to persons with T2DM.

Data Monitoring Committee: No

1.2. Schema

^aThe following circumstances are permitted: 1. Treatment will be started with dulaglutide 1.5 mg as combination therapy or dulaglutide 0.75 mg as combination therapy or monotherapy. For patients who report GI adverse events after starting treatment with 1.5 mg of dulaglutide, the investigator may reduce the dose to 0.75 mg based on symptoms reported by patients. Treatment will be continued with 0.75 mg for 2-3 weeks. Thereafter, 1.5 mg dose will be reintroduced. 2. As per common practice in India, treatment may be started with 0.75 mg of dulaglutide as a combination therapy in select cases. The dose may be up titrated to 1.5 mg after a period of 2 to 4 weeks in consultation with the medical monitor.

1.3. Schedule of Activities (SoA)

	Screening	Treatment Period							Follow-Up	Comments
		1	2	3	4	5	6	7		
Visit Number	1	2	3	4	5	6	7	8	801	
Weeks from Start of Treatment	-2	0	4	8	12	16	20	24	28	
Visit Interval Tolerance (days)	±3	—	±3	±3	±3	±3	±3	±3	±3	
Visit Detail	F	F	T	T	F	T	T	F	T	T=telehealth visit F=fasting visit
Informed consent	X									The ICF must be signed by patients or their caregivers before any -protocol specific tests or procedures are performed. See Section 10.1.3 for additional details.
Inclusion or exclusion criteria, review, and confirm	X	X								The Investigator will confirm inclusion and exclusion criteria prior to enrollment and administration of first dose of study intervention.
Demographics	X									Includes ethnicity (where permissible), year of birth, gender, and race
Preexisting conditions and medical history, including relevant surgical history	X									Collect all ongoing conditions and relevant past surgical and medical history
Prespecified medical history (indication and history of interest)	X									
Prior treatments for indication	X									

Concomitant medications	X	X	X	X	X	X	X	X		
AEs	X	X	X	X	X	X	X	X	AEs are any events that occur after signing the informed consent. These will also include any AE reported after the first dose of dulaglutide.	
Hypoglycemia events	X	X	X	X	X	X	X	X	Clinical assessment based on participant history and diary entries	
Physical Evaluation										
Height	X								Participant should remove shoes.	
Weight	X	X			X			X		
Vital signs	X	X			X			X	Includes temperature, blood pressure, and pulse rate. Measure 3 times, using the same arm, after participant has been sitting at least 5 min and before ECG tracing and collection of blood samples for laboratory testing. Of the 3 measurements, the blood pressure and pulse rate values observed during the third and final measurements will be entered in the eCRF. Additional vital signs may be measured as necessary at investigator's discretion.	
Physical examination	X								This includes examination for any sensory loss, motor neuropathy, and retinopathy. Additional physical	

										examinations may be completed as necessary at investigator's discretion.
12-lead ECG (local)	X									Participants should be supine for approximately 5-10 min before ECG collections and remain supine but awake during the ECG collection. ECGs may be repeated at the investigator's discretion at any visit.
Diabetes counseling, training, and education		X			X			X		Includes SMBG and hypoglycemia (see Section 5.3). After Visit 2, conduct as needed.
Provide training on paper diary and glucometer		X			X					After Visit 2, conduct as needed. Refer to Section 4.1.
Participant Diary and Blood Glucose Meter										
Dispense paper diary and glucometer		X			X					Dispense supplies as needed. Re-dispense paper diary at Visit 5.
Diary compliance check		X	X	X	X	X	X	X		Review entries of BG and dulaglutide. If participant is not compliant, study personnel will re-educate the participant on study requirements for continued study participation.
Collect information from study diary		X	X	X	X	X	X	X		Includes SMBG results, hypoglycemic events, date, and exact time of every study drug injection.

Laboratory Tests and Sample Collections									
Hematology	X	X			X			X	
HbA1c	X	X			X			X	
Clinical chemistry	X	X			X			X	
FBG		X			X			X	
Lipid panel		X						X	
Urinalysis	X								
Serum pregnancy test	X	X							For only WOCBP
Urine pregnancy (local)		X							
The test will be done only for WOCBP. The result must be available prior to first dose of intervention.
 
Perform additional pregnancy tests if a menstrual period is missed, if there is clinical suspicion of pregnancy, or as required by local law or regulation.

Follicle-stimulating hormone	X								
Perform as needed to confirm postmenopausal status in women. Definition in Section 10.4.

eGFR (CKD-EPI)	X	X						X	
Urinary albumin/creatinine ratio		X						X	
Dosing-Related Activities									
Dosing and injection training		X			X				After Visit 2, conduct as needed.
Distribute study drug		X			X				
IMP administration		Once weekly							The first dose will be administered under medical

				supervision by the investigator or designee at the clinical site. Subsequent doses will be self-administered by participants at home.
--	--	--	--	---

Abbreviations: BG = blood glucose; CKD-EPI = chronic kidney disease-epidemiology; ECG = electrocardiogram; eGFR = estimated glomerular filtration rate; ICF = informed consent form; IMP = investigational medicinal product; SMBG = self-monitored blood glucose; WOCBP = women of childbearing potential.

2. Introduction

Dulaglutide (LY2189265; Eli Lilly and Company [Lilly], Indianapolis, IN, USA) is a long-acting GLP-1 RA that was approved on 23 December 2014 by CDSCO for the treatment of adults with T2DM.

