4.2. Scientific Rationale for Study Design

Primary endpoint

The primary measurement is the incidence of AEs, a widely used measure to study safety profiles.

Overall design

Dulaglutide is approved in India for the treatment of T2DM. Dulaglutide, like other GLP-1 RAs that are available in India, is an established mode of therapy for T2DM. The aim of this study is to investigate the AEs and SAEs that may occur when patients with T2DM take dulaglutide. Hence, a comparator group has not been considered for this study.

The most common side effects with dulaglutide are GI in nature and mainly comprise of nausea, vomiting, and/or diarrhea. These usually occur early during therapy, are mostly mild to moderate in nature, and are self-limiting over the next 2 to 4 weeks after therapy initiation. A Phase 1 study with dulaglutide in elderly patients with T2DM from has shown reduction of FBG and postprandial glucose with the first dose of dulaglutide. Statistically significant HbA1c reduction and weight loss as a secondary benefit have been seen with dulaglutide compared to placebo within 12 weeks of start of therapy in the AWARD studies and various published real-world experiences. Hence, the proposed treatment duration of 24 weeks in this study is a reasonable timeframe to observe the effects of dulaglutide both from an AE and efficacy perspective. The follow-up visit after the last dose is designed to capture any safety data that may occur after the drug is stopped.

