***Only If intractable GI side effects not amenable to treatment**

^aOnly If intractable GI side effects not amenable to treatment

Abbreviations: F2F = face to face; GI = gastrointestinal; IP = investigational product; QW = once weekly; T = telephonic.

b Refer to the process in Panel 1 for scenario. Note:

1 pack of dulaglutide contains 2 pens.

Note: Patient followed up every 4 weeks on a remote basis till V4/ V8 (F2F) or V801 which is end of study visit (T).

Note: All efforts must be taken by the investigator to ensure that patients comply to therapy.

Note: All pens that are not used must be returned to the site at Visit 5 when the patient comes back for repeat F2F visit.

Note: Dulaglutide is provided as a combination with either other antihyperglycemic medications or in combination with insulin (basal, basal plus or premixes up to twice daily insulin regimen)

Figure 6.1. IP dispensing scenarios – Scenario 1 (top panel), Scenario 2 (middle panel), and Scenario 3 (bottom panel).

Packaging and labeling

Study interventions will be supplied by Lilly in accordance with current good manufacturing practice. Study interventions will be labeled as appropriate for country requirements.

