8.3.6. Adverse Events of Special Interest

Adverse events of special interest include

- amylase and lipase $\geq 3 \times$ ULN
- pancreatitis
- medullary thyroid cancer or any other solid organ cancer

- medullary thyroid C-cell hyperplasia/neoplasm, and
- GI events including nausea and vomiting.

If either of these are reported, sites will be prompted to collect additional details. For each event, assessment of severity, duration, and investigator's opinion of relatedness to study drug and protocol procedure will be captured.

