9.4.2. Primary Endpoints Analysis

AEs (deaths, SAEs, TEAEs, and hypoglycemia, including severe hypoglycemia)

Frequency and percentage of AE occurrence (including deaths, SAEs, TEAEs, hypoglycemia, including severe hypoglycemia and GI disorders) will be presented for the study duration using safety population.

The proportion of patients with AEs and SAEs occurring within the duration of the study (24 weeks) after being administered dulaglutide 1.5 or 0.75 mg will be presented.

The proportion of patients with AEs, TEAEs, and SAEs occurring within the duration of the study (24 weeks) after being administered dulaglutide 1.5 or 0.75 mg and 95% CIs will be estimated based on normal approximation.

The incidence of AE (death, SAE, and TEAE) will be summarized. The rate per year will be assessed using a negative binomial model with the log of the study treatment exposure time as an offset variable.

The incidence of hypoglycemic AEs will be summarized. The number of hypoglycemic events per subject over the study period will be analyzed as continuous variables and will be summarized (mean, median, SD, SE, minimum, and maximum).

The rate per year of hypoglycemic events, that is, the number of hypoglycemic events per patient-year (365.25 days) will be assessed using a negative binomial model, with baseline HbA1c and baseline insulin usage as covariates and the log of the study treatment exposure time as an offset variable.

The incidence of AEs will be calculated based on the number of new AEs out of the total eligible population using the following formula:

$$\text{Number of new AEs post intervention/Total eligible population *100.}$$

Exposure-adjusted AE incidence will be presented by the severity and preferred term for the primary analysis.

It is defined as

Number of patients with new or worsened AEs during treatment period

Patient-year exposure/365.25

Patient-year exposure is counted in days up to the AE (or end of time at risk for subjects without AE).

Incidence of gastrointestinal AEs

The incidence of GI AEs per week will be plotted over time from baseline up to 24 weeks. The proportion of subjects with at least 1 GI AE will be plotted from baseline up to Week 24. A plot of prevalence by severity (mild, moderate, or severe) for nausea, vomiting, and diarrhea over the 24-week period will be provided for the rate of GI AEs.

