Three Cox proportional hazard models, each with covariates for baseline HbA1c and baseline insulin use, will be used to model the time to the first onset of nausea, vomiting, or diarrhea TEAE, respectively.

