3.1 Primary endpoints

- Incidence of AEs (deaths, SAEs, TEAEs, and hypoglycemia, including severe hypoglycemia)
- Proportion of patients reporting AEs and SAEs between baseline and Week 24
- Incidence of GI AEs

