18.3.2 Analyses

Population: FAS and PP

Stratification: Table: Add the strata as needed in case subjects with dose modification exceeding 20% based on enrolled population as per section 7.3:

- a. Subjects on 1.5 mg only
- b. Subjects on 0.75 mg only
- c. Subjects with any dose modification*

* Subjects who have received at least one dose of 1.5 mg and at least one dose of 0.75 mg

Statistics: The incidence of GI AEs will be summarised and a plot of prevalence by severity (mild, moderate, or severe) for nausea, vomiting, and diarrhoea over the 24-week period will be provided for the rate of GI AEs. Plot of severity with reference to time will be provided by subjects.

Three Cox proportional hazard models, each with covariates for baseline HbA1c and baseline insulin use, will be used to model the time to the first onset of nausea, vomiting, or diarrhoea TEAE,

respectively. Hazard ratio and 95% confidence interval and p-value will be presented for the covariates for the overall data. If additional analysis based of dose stratification is done, the Hazard ratio and 95% confidence interval and p-value will also be presented for dose with 1.5 mg as the reference group.

Subjects who do not experience any GI AEs during 24 weeks and discontinued before 24 weeks of period will be considered as censored.

The Kaplan Meier plot (unadjusted) will be presented for median time to first onset of nausea, vomiting, or diarrhoea TEAE, respectively along with corresponding 95% confidence interval. Y axis will represent the survival probability of the GI AEs and X axis will represent the duration in days of GI event occurred from first dose administration. Number of subjects at risk will be presented in the plot.

Additionally, all the analysis will be repeated for the below mentioned subgroups:

- age (<65 year and \geq 65 year)
- HbA1c (<8.5 and \geq 8.5)
- Sex (Female and male)
- BMI category (<27 kg/m²) and \geq 27 kg/m²)

19. Secondary endpoint**19.1 Mean change in HbA1c from baseline to Week 24****19.1.1 Variables and derivations**

Variables:

- HbA1c results

Derivations:

- HbA1c results between visit baseline visit 2 (week 0) and visit 8 (week 24) will be used.

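### GI adverse events are a primary endpoint with week- and day-level analyses, but no listed diary item records symptoms and the first scheduled contact after the first dose is at Week 4, so early events not reported unprompted rest on up to 4 weeks of recall

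*Protocol*

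**What the plan says.** Both documents list "Incidence of GI AEs" among the primary endpoints (Protocol Section 3, SAP Section 3.1). The planned analyses need dates:

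- Protocol Section 9.4.2: "The incidence of GI AEs per week will be plotted over time from baseline up to 24 weeks", and a plot of prevalence by severity for nausea, vomiting and diarrhea over the 24 weeks.
- The same section: three Cox models that "will be used to model the time to the first onset of nausea, vomiting, or diarrhea TEAE, respectively".
- SAP Section 18.3.2: Kaplan-Meier curves whose "X axis will represent the duration in days of GI event occurred from first dose administration", plus a per-subject plot of severity against time.
- Protocol Section 8.3.6 counts GI events as events of special interest: "For each event, assessment of severity, duration, and investigator's opinion of relatedness to study drug and protocol procedure will be captured".

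On collection, the Schedule of Activities (Protocol Section 1.3) says of the diary data: "Includes SMBG results, hypoglycemic events, date, and exact time of every study drug injection". The diary compliance check covers blood glucose and dulaglutide entries. Adverse events are otherwise elicited by open, non-leading verbal questioning (Protocol Section 8.3). Visit 3, by telehealth at Week 4 ±3 days, is the first scheduled contact after dosing starts at Visit 2. The notes to Figure 6.1 give the same rhythm: "Patient followed up every 4 weeks on a remote basis".

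Protocol Section 4.2 describes the expected GI effects: "These usually occur early during therapy, are mostly mild to moderate in nature, and are self-limiting over the next 2 to 4 weeks".

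**The concern.** The schedule of questioning does not match the expected course of the events. If GI effects start early and settle within 2 to 4 weeks, many will be over, or nearly so, before anyone is scheduled to ask. Unless the patient calls the site, onset day, stop day and severity are then reconstructed from memory.

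Two kinds of error follow. First, mild events that have resolved are the easiest to forget, so reported incidence is likely too low and the remaining events look more severe than the full set. Sampling error does not cover this, because the bias runs in one direction and the confidence interval does not reflect it. Second, approximate onset dates blur the weekly plot, the prevalence curves and the time-to-onset analyses. The study exists to document local safety experience for a marketing-authorization clause, and GI effects are the main expected harm.

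**Working it through.** **Plan's own figures.** The only sample-size chain is 250 screened, 200 started and about 160 completing (Protocol Section 9.6). It reproduces: 160/(1 − 0.20) = 200 and 200/(1 − 0.20) = 250. The point does not depend on it, except that n = 200 is used below.

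**Recall window (from the documents).** The first scheduled contact is Day 28, or Day 25 to 31 with the tolerance. Later gaps are 28 days, or 22 to 34 with tolerance at both ends. Recall = contact day − onset day. At a Day 28 contact:

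| Onset in | Recall (days) |
|---|---|
| Week 1 | 21 to 28 |
| Week 2 | 14 to 21 |
| Week 3 | 7 to 14 |
| Week 4 | 0 to 7 |

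If onset is uniform over Days 0 to 28, mean recall is 28 − 14 = 14 days. If it is uniform over Days 0 to 14, mean recall is 28 − 7 = 21 days. Four weeks is the maximum.

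**Share over by Day 28 (assumption: exponential duration, mean m of 5 or 10 days).**
- Onset uniform on Days 0 to 14: 1 − (m/14)(e^(−14/m) − e^(−28/m)) = 98% for m = 5 and 87% for m = 10.
- Onset uniform on Days 0 to 28: 1 − (m/28)(1 − e^(−28/m)) = 82% for m = 5 and 66% for m = 10.

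Under all four settings, most events have ended before the first scheduled question.

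**Misdating (assumption: normal recall error, onset uniform over 28 days, 400,000 simulated onsets).** With an error SD of 2, 3, 5 or 7 days, 17%, 25%, 39% or 47% of onsets land in the wrong week. The SDs are assumed. The documents give none.

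**Under-capture (assumptions: true incidence 30%; 50% to 70% of cases mild; 10% to 30% of mild cases missed; no others missed).** Observed = 0.30 × (1 − mild share × share missed).
- Smallest loss: 0.30 × (1 − 0.5 × 0.1) = 28.5%.
- Largest loss: 0.30 × (1 − 0.7 × 0.3) = 23.7%.

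The bias is 1.5 to 6.3 percentage points. The 95% half-width at n = 200 is 1.96 × √(0.3 × 0.7/200) = 6.4 points.

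**Severity mix (same assumptions).** Observed mild share = mild share × (1 − missed)/(1 − mild share × missed). At 50% mild and 30% missed this is 0.35/0.85 = 41%. At 70% mild and 30% missed it is 0.49/0.79 = 62%.

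**The case against.** Several points on the other side stand.

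- **The diary form is not in the documents.** The listed items open with an inclusive word, so the absence of symptoms is an inference. It is a well-supported one. The compliance check names only glucose and dulaglutide. Protocol Section 8.1 describes the diary for hypoglycemia data. The Schedule of Activities names diary entries as a source for hypoglycemia but not for adverse events. The amendment log removed insulin dose from the compliance check because the diary had no place for it, which suggests that the row was compared with the form.
- **Unprompted reports are expected.** Protocol Section 6.5 provides for patients who report GI events early in treatment, and the Figure 6.1 flow is not shown. A reader might infer that every GI event rests on 4 weeks of recall. The documents do not support that: some events will be reported when they happen. These are more likely to be the troublesome ones, which leaves mild events to recall.
- **Memory has an anchor.** The dated weekly injection may make recall errors smaller than those assumed.
- **The consequence is bounded.** The study is single-arm and descriptive, without a hypothesis. Cumulative incidence over 24 weeks needs no exact onset date, and a patient leaves that count only if every GI event is forgotten. SAP Section 18.3.2 does not repeat the weekly incidence plot, although SAP Section 5 states that the planned analyses are unchanged.

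Two stronger readings fail. A reader might infer that the reported interval would exclude the truth. With 60 of 200 truly affected, the Clopper-Pearson interval is 21.0% to 33.7% at 54 reported and 18.3% to 30.5% at 48. It excludes 30% only once at least 13 of the 60 are missed (47 of 200: upper limit 29.996%). The documents give no basis for assuming that. A reader might also infer that events cannot be tied to a dose because the diary list omits pen strength. But SAP Section 12 plans an exposure eCRF page and a per-subject plot of dose over time. The dose strata in SAP Section 7.3 are per subject, and no planned GI analysis assigns an event to the dose at onset.

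The partial-date imputation in SAP Section 15.1 is a general convention for all adverse events. It is no evidence that GI dates in particular will be missing.

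**Conclusion.** The mismatch is real and should be corrected. GI incidence is a primary endpoint with week- and day-level outputs. The listed diary data name no symptoms, and scheduled questioning starts at Week 4, when by the protocol's own account many early events will have settled. For events not reported unprompted, recall runs up to 4 weeks, with a mean of about 2 to 3 weeks depending on the onset pattern assumed.

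The likely direction is low incidence, a severity mix shifted upward and approximate onset dates. The size is unknown. The 23.7% to 28.5% observed against a true 30%, and the 17% to 47% of onsets in the wrong week, are illustrations on stated assumptions. The conclusion also assumes that the diary form matches its description in the Schedule of Activities and that Figure 6.1 adds no earlier scheduled calls. Its own note on follow-up every 4 weeks supports the latter.

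**What to change.** In the diary row of the Schedule of Activities and on the diary form, add one open, non-leading line: any health problem, with start date, stop date and how bad it was. Review it at every contact already scheduled, and use it as a source for adverse-event onset and stop dates in the CRF. The open wording keeps to the non-leading approach in Protocol Section 8.3, and diary data are already transcribed to the eCRF (Protocol Section 10.1.6). No new visit, no change in sample size and no change in clinical management is needed.

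The cost is a diary reprint, an edited Schedule of Activities comment and a short protocol amendment. The downsides are slightly more diary burden and more mild events recorded. A paper diary can also still be back-filled before a call, so the line reduces recall error without removing it.
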